### 14.2.2 Labile Plasma Iron ( $\mu$ M)

Table 14.2.2.1 LPI ( $\mu$ M) each assessment – ITT population

	Deferiprone		Placebo		P-value (t-test)
	N	Mean $\pm$ SD (Min, Max)	N	Mean $\pm$ SD (Min, Max)	
Baseline	xx	x.xx $\pm$ x.xx (x.xx, x.xx)	xx	x.xx $\pm$ x.xx (x.xx, x.xx)	0xxxx
Month 1	xx	x.xx $\pm$ x.xx (x.xx, x.xx)	xx	x.xx $\pm$ x.xx (x.xx, x.xx)	0xxxx
Month 2	xx	x.xx $\pm$ x.xx (x.xx, x.xx)	xx	x.xx $\pm$ x.xx (x.xx, x.xx)	0xxxx
Month 3	xx	x.xx $\pm$ x.xx (x.xx, x.xx)	xx	x.xx $\pm$ x.xx (x.xx, x.xx)	0xxxx
Month 4	xx	x.xx $\pm$ x.xx (x.xx, x.xx)	xx	x.xx $\pm$ x.xx (x.xx, x.xx)	0xxxx
Month 5	xx	x.xx $\pm$ x.xx (x.xx, x.xx)	xx	x.xx $\pm$ x.xx (x.xx, x.xx)	0xxxx
Month 6	xx	x.xx $\pm$ x.xx (x.xx, x.xx)	xx	x.xx $\pm$ x.xx (x.xx, x.xx)	0xxxx
Month 7	xx	x.xx $\pm$ x.xx (x.xx, x.xx)	xx	x.xx $\pm$ x.xx (x.xx, x.xx)	0xxxx
Month 8	xx	x.xx $\pm$ x.xx (x.xx, x.xx)	xx	x.xx $\pm$ x.xx (x.xx, x.xx)	0xxxx
Month 9	xx	x.xx $\pm$ x.xx (x.xx, x.xx)	xx	x.xx $\pm$ x.xx (x.xx, x.xx)	0xxxx
Month 10	xx	x.xx $\pm$ x.xx (x.xx, x.xx)	xx	x.xx $\pm$ x.xx (x.xx, x.xx)	0xxxx
Month 11	xx	x.xx $\pm$ x.xx (x.xx, x.xx)	xx	x.xx $\pm$ x.xx (x.xx, x.xx)	0xxxx
Month 12	xx	x.xx $\pm$ x.xx (x.xx, x.xx)	xx	x.xx $\pm$ x.xx (x.xx, x.xx)	0xxxx

Data source: 16.2.6.1 Listing of labile plasma iron (LPI)

Note: Similar Table 14.2.2.1a will be made for PP population

Table 14.2.2.2 Change in LPI ( $\mu$ M) from baseline to each follow-up assessment – ITT population

	Deferiprone		Placebo		P-value (t-test)
	N	Mean $\pm$ SD (Min, Max)	N	Mean $\pm$ SD (Min, Max)	
Month 1	xx	x.xx $\pm$ x.xx (x.xx, x.xx)	xx	x.xx $\pm$ x.xx (x.xx, x.xx)	0xxxx
Month 2	xx	x.xx $\pm$ x.xx (x.xx, x.xx)	xx	x.xx $\pm$ x.xx (x.xx, x.xx)	0xxxx
Month 3	xx	x.xx $\pm$ x.xx (x.xx, x.xx)	xx	x.xx $\pm$ x.xx (x.xx, x.xx)	0xxxx
Month 4	xx	x.xx $\pm$ x.xx (x.xx, x.xx)	xx	x.xx $\pm$ x.xx (x.xx, x.xx)	0xxxx
Month 5	xx	x.xx $\pm$ x.xx (x.xx, x.xx)	xx	x.xx $\pm$ x.xx (x.xx, x.xx)	0xxxx
Month 6	xx	x.xx $\pm$ x.xx (x.xx, x.xx)	xx	x.xx $\pm$ x.xx (x.xx, x.xx)	0xxxx
Month 7	xx	x.xx $\pm$ x.xx (x.xx, x.xx)	xx	x.xx $\pm$ x.xx (x.xx, x.xx)	0xxxx
Month 8	xx	x.xx $\pm$ x.xx (x.xx, x.xx)	xx	x.xx $\pm$ x.xx (x.xx, x.xx)	0xxxx
Month 9	xx	x.xx $\pm$ x.xx (x.xx, x.xx)	xx	x.xx $\pm$ x.xx (x.xx, x.xx)	0xxxx
Month 10	xx	x.xx $\pm$ x.xx (x.xx, x.xx)	xx	x.xx $\pm$ x.xx (x.xx, x.xx)	0xxxx
Month 11	xx	x.xx $\pm$ x.xx (x.xx, x.xx)	xx	x.xx $\pm$ x.xx (x.xx, x.xx)	0xxxx
Month 12	xx	x.xx $\pm$ x.xx (x.xx, x.xx)	xx	x.xx $\pm$ x.xx (x.xx, x.xx)	0xxxx

Data source: 16.2.6.1 Listing of labile plasma iron (LPI)

Note: Similar Table 14.2.2.1a will be made for PP population

Table 14.2.2.3 LS Means for change in LPI ( $\mu\text{M}$ ) from ANCOVA model at each follow-up assessment – ITT population

	Deferiprone	Placebo	Deferiprone Minus Placebo	95% C.I.
N	xx	xx	xx	
	LS Mean $\pm$ SE	LS Mean $\pm$ SE	LS Mean $\pm$ SE	
Month 1	x.xx $\pm$ x.xx	x.xx $\pm$ x.xx	x.xx $\pm$ x.xx	(x.xx, x.xx)
Month 2	x.xx $\pm$ x.xx	x.xx $\pm$ x.xx	x.xx $\pm$ x.xx	(x.xx, x.xx)
Month 3	x.xx $\pm$ x.xx	x.xx $\pm$ x.xx	x.xx $\pm$ x.xx	(x.xx, x.xx)
Month 4	x.xx $\pm$ x.xx	x.xx $\pm$ x.xx	x.xx $\pm$ x.xx	(x.xx, x.xx)
Month 5	x.xx $\pm$ x.xx	x.xx $\pm$ x.xx	x.xx $\pm$ x.xx	(x.xx, x.xx)
Month 6	x.xx $\pm$ x.xx	x.xx $\pm$ x.xx	x.xx $\pm$ x.xx	(x.xx, x.xx)
Month 7	x.xx $\pm$ x.xx	x.xx $\pm$ x.xx	x.xx $\pm$ x.xx	(x.xx, x.xx)
Month 8	x.xx $\pm$ x.xx	x.xx $\pm$ x.xx	x.xx $\pm$ x.xx	(x.xx, x.xx)
Month 9	x.xx $\pm$ x.xx	x.xx $\pm$ x.xx	x.xx $\pm$ x.xx	(x.xx, x.xx)
Month 10	x.xx $\pm$ x.xx	x.xx $\pm$ x.xx	x.xx $\pm$ x.xx	(x.xx, x.xx)
Month 11	x.xx $\pm$ x.xx	x.xx $\pm$ x.xx	x.xx $\pm$ x.xx	(x.xx, x.xx)
Month 12	x.xx $\pm$ x.xx	x.xx $\pm$ x.xx	x.xx $\pm$ x.xx	(x.xx, x.xx)

Data source: 16.2.6.1 Listing of labile plasma iron (LPI)

Note: Similar Table 14.2.2.3a will be made for PP population

Table 14.2.2.4 Trend analysis for LPI ( $\mu$ M) over time – ITT population

Rate of change per month	Deferiprone	Placebo	Deferiprone minus Placebo	P-value
Mean $\pm$ SE	$x.xx \pm x.xx$	$x.xx \pm x.xx$	$x.xx \pm x.xx$	0.xxxx

Data source: 16.2.6.1 Listing of labile plasma iron (LPI)

Note: Similar Table 14.2.2.4a will be made for PP population

Table 14.2.2.5 Percent of patients who had LPI  $< 0.6 \mu$ M at each assessment – ITT population

	Deferiprone	Placebo	P-value (Fisher's exact test)
Baseline	xx% (xx / xx)	xx% (xx / xx)	0.xxxx
Month 1	xx% (xx / xx)	xx% (xx / xx)	0.xxxx
Month 2	xx% (xx / xx)	xx% (xx / xx)	0.xxxx
Month 3	xx% (xx / xx)	xx% (xx / xx)	0.xxxx
Month 4	xx% (xx / xx)	xx% (xx / xx)	0.xxxx
Month 5	xx% (xx / xx)	xx% (xx / xx)	0.xxxx
Month 6	xx% (xx / xx)	xx% (xx / xx)	0.xxxx
Month 7	xx% (xx / xx)	xx% (xx / xx)	0.xxxx
Month 8	xx% (xx / xx)	xx% (xx / xx)	0.xxxx
Month 9	xx% (xx / xx)	xx% (xx / xx)	0.xxxx
Month 10	xx% (xx / xx)	xx% (xx / xx)	0.xxxx
Month 11	xx% (xx / xx)	xx% (xx / xx)	0.xxxx
Month 12	xx% (xx / xx)	xx% (xx / xx)	0.xxxx

Data source: 16.2.6.1 Listing of labile plasma iron (LPI)

Note: Similar Table 14.2.2.5a will be made for PP population

### 14.2.3 Transferrin Saturation (%)

Table 14.2.3.1 TSAT (%) each assessment – ITT population

	Deferiprone		Placebo		P-value (t-test)
	N	Mean ± SD (Min, Max)	N	Mean ± SD (Min, Max)	
Baseline	xx	xx.x ± xx.x (xx.x, xx.x)	xx	xx.x ± xx.x (xx.x, x.xx)	0xxxx
Month 1	xx	xx.x ± xx.x (xx.x, xx.x)	xx	xx.x ± xx.x (xx.x, x.xx)	0xxxx
Month 2	xx	xx.x ± xx.x (xx.x, xx.x)	xx	xx.x ± xx.x (xx.x, x.xx)	0xxxx
Month 3	xx	xx.x ± xx.x (xx.x, xx.x)	xx	xx.x ± xx.x (xx.x, x.xx)	0xxxx
Month 4	xx	xx.x ± xx.x (xx.x, xx.x)	xx	xx.x ± xx.x (xx.x, x.xx)	0xxxx
Month 5	xx	xx.x ± xx.x (xx.x, xx.x)	xx	xx.x ± xx.x (xx.x, x.xx)	0xxxx
Month 6	xx	xx.x ± xx.x (xx.x, xx.x)	xx	xx.x ± xx.x (xx.x, x.xx)	0xxxx
Month 7	xx	xx.x ± xx.x (xx.x, xx.x)	xx	xx.x ± xx.x (xx.x, x.xx)	0xxxx
Month 8	xx	xx.x ± xx.x (xx.x, xx.x)	xx	xx.x ± xx.x (xx.x, x.xx)	0xxxx
Month 9	xx	xx.x ± xx.x (xx.x, xx.x)	xx	xx.x ± xx.x (xx.x, x.xx)	0xxxx
Month 10	xx	xx.x ± xx.x (xx.x, xx.x)	xx	xx.x ± xx.x (xx.x, x.xx)	0xxxx
Month 11	xx	xx.x ± xx.x (xx.x, xx.x)	xx	xx.x ± xx.x (xx.x, x.xx)	0xxxx
Month 12	xx	xx.x ± xx.x (xx.x, xx.x)	xx	xx.x ± xx.x (xx.x, x.xx)	0xxxx

Data source: 16.2.6.3 Listing of transferrin saturation (TSAT)

Note: Similar Table 14.2.3.1a will be made for PP population

Table 14.2.3.2 Change in TSAT (%) from baseline to each follow-up assessment – ITT population

	Deferiprone		Placebo		
	N	Mean ± SD (Min, Max)	N	Mean ± SD (Min, Max)	P-value (t-test)
Month 1	xx	xx.x ± xx.x (xx.x, xx.x)	xx	xx.x ± xx.x (xx.x, x.xx)	0xxxx
Month 2	xx	xx.x ± xx.x (xx.x, xx.x)	xx	xx.x ± xx.x (xx.x, x.xx)	0xxxx
Month 3	xx	xx.x ± xx.x (xx.x, xx.x)	xx	xx.x ± xx.x (xx.x, x.xx)	0xxxx
Month 4	xx	xx.x ± xx.x (xx.x, xx.x)	xx	xx.x ± xx.x (xx.x, x.xx)	0xxxx
Month 5	xx	xx.x ± xx.x (xx.x, xx.x)	xx	xx.x ± xx.x (xx.x, x.xx)	0xxxx
Month 6	xx	xx.x ± xx.x (xx.x, xx.x)	xx	xx.x ± xx.x (xx.x, x.xx)	0xxxx
Month 7	xx	xx.x ± xx.x (xx.x, xx.x)	xx	xx.x ± xx.x (xx.x, x.xx)	0xxxx
Month 8	xx	xx.x ± xx.x (xx.x, xx.x)	xx	xx.x ± xx.x (xx.x, x.xx)	0xxxx
Month 9	xx	xx.x ± xx.x (xx.x, xx.x)	xx	xx.x ± xx.x (xx.x, x.xx)	0xxxx
Month 10	xx	xx.x ± xx.x (xx.x, xx.x)	xx	xx.x ± xx.x (xx.x, x.xx)	0xxxx
Month 11	xx	xx.x ± xx.x (xx.x, xx.x)	xx	xx.x ± xx.x (xx.x, x.xx)	0xxxx
Month 12	xx	xx.x ± xx.x (xx.x, xx.x)	xx	xx.x ± xx.x (xx.x, x.xx)	0xxxx

Data source: 16.2.6.3 Listing of transferrin saturation (TSAT)

Note: Similar Table 14.2.3.2a will be made for PP population

Table 14.2.3.3 LS Means for change in TSAT (%) from ANCOVA model at each follow-up assessment – ITT population

	Deferiprone	Placebo	Deferiprone Minus Placebo	95% C.I.
N	xx	xx	xx	
	LS Mean ± SE	LS Mean ± SE	LS Mean ± SE	
Month 1	xx.x ± xx.x	xx.x ± xx.x	xx.x ± xx.x	(xx.x, xx.x)
Month 2	xx.x ± xx.x	xx.x ± xx.x	xx.x ± xx.x	(xx.x, xx.x)
Month 3	xx.x ± xx.x	xx.x ± xx.x	xx.x ± xx.x	(xx.x, xx.x)
Month 4	xx.x ± xx.x	xx.x ± xx.x	xx.x ± xx.x	(xx.x, xx.x)
Month 5	xx.x ± xx.x	xx.x ± xx.x	xx.x ± xx.x	(xx.x, xx.x)
Month 6	xx.x ± xx.x	xx.x ± xx.x	xx.x ± xx.x	(xx.x, xx.x)
Month 7	xx.x ± xx.x	xx.x ± xx.x	xx.x ± xx.x	(xx.x, xx.x)
Month 8	xx.x ± xx.x	xx.x ± xx.x	xx.x ± xx.x	(xx.x, xx.x)
Month 9	xx.x ± xx.x	xx.x ± xx.x	xx.x ± xx.x	(xx.x, xx.x)
Month 10	xx.x ± xx.x	xx.x ± xx.x	xx.x ± xx.x	(xx.x, xx.x)
Month 11	xx.x ± xx.x	xx.x ± xx.x	xx.x ± xx.x	(xx.x, xx.x)
Month 12	xx.x ± xx.x	xx.x ± xx.x	xx.x ± xx.x	(xx.x, xx.x)

Data source: 16.2.6.3 Listing of transferrin saturation (TSAT)

Note: Similar Table 14.2.3.3a will be made for PP population

Table 14.2.3.4 Trend analysis for TSAT (%) over time – ITT population

Rate of change per month	Deferiprone	Placebo	Deferiprone minus Placebo	P-value
Mean ± SE	xx.x ± xx.x	xx.x ± xx.x	xx.x ± xx.x	0xxxx

Data source: 16.2.6.3 Listing of transferrin saturation (TSAT)

Note: Similar Table 14.2.3.4a will be made for PP population

Table 14.2.3.5 Percent of patients who had TSAT < 60% at each assessment – ITT population

	Deferiprone	Placebo	P-value (Fisher's exact test)
Baseline	xx% (xx / xx)	xx% (xx / xx)	0xxxx
Month 1	xx% (xx / xx)	xx% (xx / xx)	0xxxx
Month 2	xx% (xx / xx)	xx% (xx / xx)	0xxxx
Month 3	xx% (xx / xx)	xx% (xx / xx)	0xxxx
Month 4	xx% (xx / xx)	xx% (xx / xx)	0xxxx
Month 5	xx% (xx / xx)	xx% (xx / xx)	0xxxx
Month 6	xx% (xx / xx)	xx% (xx / xx)	0xxxx
Month 7	xx% (xx / xx)	xx% (xx / xx)	0xxxx
Month 8	xx% (xx / xx)	xx% (xx / xx)	0xxxx
Month 9	xx% (xx / xx)	xx% (xx / xx)	0xxxx
Month 10	xx% (xx / xx)	xx% (xx / xx)	0xxxx
Month 11	xx% (xx / xx)	xx% (xx / xx)	0xxxx
Month 12	xx% (xx / xx)	xx% (xx / xx)	0xxxx

Data source: 16.2.6.3 Listing of transferrin saturation (TSAT)

Note: Similar Table 14.2.3.5a will be made for PP population

## 14.3 Safety analyses

### 14.3.1 Adverse events

Table 14.3.1.1 Overall summary of adverse events

	Deferiprone	Placebo	
N	xxx	xxx	P-value
Number of patients experiencing at least one AE	xx (xx%)	xx (xx%)	0.xxxx
Number of patients experiencing at least one severe AE	xx (xx%)	xx (xx%)	0.xxxx
Number of patients experiencing at least one serious AE	xx (xx%)	xx (xx%)	0.xxxx
Number of patients experiencing at least one related* AE	xx (xx%)	xx (xx%)	0.xxxx
Number of patient deaths	xx (xx%)	xx (xx%)	0.xxxx
Number of patient withdrawals due to AEs	xx (xx%)	xx (xx%)	0.xxxx

\*Includes possibly, probably, and definitely related. Worst case scenario of causality between the investigator and company's assessment.

Data source: 16.2.7.2 Listing of adverse events

Table14.3.1.2 Adverse events

	Deferiprone (N=xx)	Placebo (N=xx)	Fisher's exact test
	Exposure (Patient-years):x.xx	Exposure (Patient-years):x.xx	
	Total Events: xxx	Total Events: xxx	
System Organ Class Preferred Term	n Patients (%)	n Patients (%)	p-value
CCCCCCC	x (x.x)	x (x.x)	0xxxx
Ccccccc	x (x.x)	x (x.x)	0xxxx
Ccccccc	x (x.x)	x (x.x)	0xxxx
Ccccccc	x (x.x)	x (x.x)	0xxxx
.....	.....	.....	.....

Data source: 16.2.7.2 Listing of adverse events

Note: Similar Table 14.3.1.2 to Table 14.3.1.11 will be produced.

Table 14.3.1.12 Adverse events by causality

		Deferiprone (N=xx)	Placebo (N=xx)
System Organ Class Preferred Term	Relatedness (worst case)	Patients reporting (n=xx)	Patients reporting (n=xx)
CCCCCCCC		x (x.x)	x (x.x)
ccccc	Not Related	x (x.x)	x (x.x)
	Related*	x (x.x)	x (x.x)
cccccc	Not Related	x (x.x)	x (x.x)
	Related*	x (x.x)	x (x.x)
.....	.....	.....	.....

\*Possibly, Probably, or Definitely Related

Data source: 16.2.7.2 Listing of adverse events

Table 14.3.1.13 Adverse events – event count and rate

System Organ Class Preferred Term	Deferiprone (N=xx)	Placebo (N=xx)
	Exposure (Patient-years):x.xx	Exposure (Patient-years):x.xx
	Total Events (Rate/100 patient- years): xx (x.xx)	Total Events (Rate/100 patient- years): xx (x.xx)
CCCCCCC	xx (x.xx)	(x.xx)
Cccccc	xx (x.xx)	xx (x.xx)
Ccccccc	xx (x.xx)	xx (x.xx)
Ccccccc	xx (x.xx)	xx (x.xx)
.....	.....	.....

Data source: 16.2.7.2 Listing of adverse events

### 14.3.2 Vital signs

Table 14.3.2.1 Temperature (C) at each assessment

	Deferiprone		Placebo		P-value (t-test)
	N	Mean $\pm$ SD (Min, Max)	N	Mean $\pm$ SD (Min, Max)	
Baseline	xx	xx.x $\pm$ xx.x (xx.x,xx.x)	xx	xx.x $\pm$ xx.x (xx.x,xx.x)	0xxxx
Month 1	xx	xx.x $\pm$ xx.x (xx.x,xx.x)	xx	xx.x $\pm$ xx.x (xx.x,xx.x)	0xxxx
Month 2	xx	xx.x $\pm$ xx.x (xx.x,xx.x)	xx	xx.x $\pm$ xx.x (xx.x,xx.x)	0xxxx
Month 3	xx	xx.x $\pm$ xx.x (xx.x,xx.x)	xx	xx.x $\pm$ xx.x (xx.x,xx.x)	0xxxx
Month 4	xx	xx.x $\pm$ xx.x (xx.x,xx.x)	xx	xx.x $\pm$ xx.x (xx.x,xx.x)	0xxxx
Month 5	xx	xx.x $\pm$ xx.x (xx.x,xx.x)	xx	xx.x $\pm$ xx.x (xx.x,xx.x)	0xxxx
Month 6	xx	xx.x $\pm$ xx.x (xx.x,xx.x)	xx	xx.x $\pm$ xx.x (xx.x,xx.x)	0xxxx
Month 7	xx	xx.x $\pm$ xx.x (xx.x,xx.x)	xx	xx.x $\pm$ xx.x (xx.x,xx.x)	0xxxx
Month 8	xx	xx.x $\pm$ xx.x (xx.x,xx.x)	xx	xx.x $\pm$ xx.x (xx.x,xx.x)	0xxxx
Month 9	xx	xx.x $\pm$ xx.x (xx.x,xx.x)	xx	xx.x $\pm$ xx.x (xx.x,xx.x)	0xxxx
Month 10	xx	xx.x $\pm$ xx.x (xx.x,xx.x)	xx	xx.x $\pm$ xx.x (xx.x,xx.x)	0xxxx
Month 11	xx	xx.x $\pm$ xx.x (xx.x,xx.x)	xx	xx.x $\pm$ xx.x (xx.x,xx.x)	0xxxx
Month 12	xx	xx.x $\pm$ xx.x (xx.x,xx.x)	xx	xx.x $\pm$ xx.x (xx.x,xx.x)	0xxxx

Data source: 16.2.9.5 Listing of vital signs

Note: Similar Tables 14.3.2.3, 14.3.2.5, and 14.3.2.7 for heart rate, diastolic blood pressure, and systolic blood pressure will be produced, respectively.

Table 14.3.2.2 Change in temperature (C) from baseline to at each follow-up assessment

	Deferiprone		Placebo		
	N	Mean ± SD (Min, Max)	N	Mean ± SD (Min, Max)	P-value (t-test)
Month 1	xx	xx.x ± xx.x (xx.x,xx.x)	xx	xx.x ± xx.x (xx.x,xx.x)	0xxxx
Month 2	xx	xx.x ± xx.x (xx.x,xx.x)	xx	xx.x ± xx.x (xx.x,xx.x)	0xxxx
Month 3	xx	xx.x ± xx.x (xx.x,xx.x)	xx	xx.x ± xx.x (xx.x,xx.x)	0xxxx
Month 4	xx	xx.x ± xx.x (xx.x,xx.x)	xx	xx.x ± xx.x (xx.x,xx.x)	0xxxx
Month 5	xx	xx.x ± xx.x (xx.x,xx.x)	xx	xx.x ± xx.x (xx.x,xx.x)	0xxxx
Month 6	xx	xx.x ± xx.x (xx.x,xx.x)	xx	xx.x ± xx.x (xx.x,xx.x)	0xxxx
Month 7	xx	xx.x ± xx.x (xx.x,xx.x)	xx	xx.x ± xx.x (xx.x,xx.x)	0xxxx
Month 8	xx	xx.x ± xx.x (xx.x,xx.x)	xx	xx.x ± xx.x (xx.x,xx.x)	0xxxx
Month 9	xx	xx.x ± xx.x (xx.x,xx.x)	xx	xx.x ± xx.x (xx.x,xx.x)	0xxxx
Month 10	xx	xx.x ± xx.x (xx.x,xx.x)	xx	xx.x ± xx.x (xx.x,xx.x)	0xxxx
Month 11	xx	xx.x ± xx.x (xx.x,xx.x)	xx	xx.x ± xx.x (xx.x,xx.x)	0xxxx
Month 12	xx	xx.x ± xx.x (xx.x,xx.x)	xx	xx.x ± xx.x (xx.x,xx.x)	0xxxx

Data source: 16.2.9.5 Listing of vital signs

Note: Similar Tables 14.3.2.4, 14.3.2.6, 14.3.2.8 for heart rate, diastolic, and systolic blood pressure will be produced, respectively.

### 14.3.3 Height

Table 14.3.3.1 Height (cm) at each assessment

	Deferiprone		Placebo		P-value (t-test)
	N	Mean ± SD (Min, Max)	N	Mean ± SD (Min, Max)	
Baseline	xx	xxx ± xxx (xxx, xxx)	xx	xxx ± xxx (xxx, xxx)	0xxxx
Month 1	xx	xxx ± xxx (xxx, xxx)	xx	xxx ± xxx (xxx, xxx)	0xxxx
Month 2	xx	xxx ± xxx (xxx, xxx)	xx	xxx ± xxx (xxx, xxx)	0xxxx
Month 3	xx	xxx ± xxx (xxx, xxx)	xx	xxx ± xxx (xxx, xxx)	0xxxx
Month 4	xx	xxx ± xxx (xxx, xxx)	xx	xxx ± xxx (xxx, xxx)	0xxxx
Month 5	xx	xxx ± xxx (xxx, xxx)	xx	xxx ± xxx (xxx, xxx)	0xxxx
Month 6	xx	xxx ± xxx (xxx, xxx)	xx	xxx ± xxx (xxx, xxx)	0xxxx
Month 7	xx	xxx ± xxx (xxx, xxx)	xx	xxx ± xxx (xxx, xxx)	0xxxx
Month 8	xx	xxx ± xxx (xxx, xxx)	xx	xxx ± xxx (xxx, xxx)	0xxxx
Month 9	xx	xxx ± xxx (xxx, xxx)	xx	xxx ± xxx (xxx, xxx)	0xxxx
Month 10	xx	xxx ± xxx (xxx, xxx)	xx	xxx ± xxx (xxx, xxx)	0xxxx
Month 11	xx	xxx ± xxx (xxx, xxx)	xx	xxx ± xxx (xxx, xxx)	0xxxx
Month 12	xx	xxx ± xxx (xxx, xxx)	xx	xxx ± xxx (xxx, xxx)	0xxxx

Data source: 16.2.9.5 Listing of vital signs

Table 14.3.3.2 Change in height (cm) from baseline to at each follow-up assessment

	Deferiprone		Placebo		
	N	Mean ± SD (Min, Max)	N	Mean ± SD (Min, Max)	P-value (t-test)
Month 1	xx	xxx ± xxx (xxx, xxx)	xx	xxx ± xxx (xxx, xxx)	0.xxxx
Month 2	xx	xxx ± xxx (xxx, xxx)	xx	xxx ± xxx (xxx, xxx)	0.xxxx
Month 3	xx	xxx ± xxx (xxx, xxx)	xx	xxx ± xxx (xxx, xxx)	0.xxxx
Month 4	xx	xxx ± xxx (xxx, xxx)	xx	xxx ± xxx (xxx, xxx)	0.xxxx
Month 5	xx	xxx ± xxx (xxx, xxx)	xx	xxx ± xxx (xxx, xxx)	0.xxxx
Month 6	xx	xxx ± xxx (xxx, xxx)	xx	xxx ± xxx (xxx, xxx)	0.xxxx
Month 7	xx	xxx ± xxx (xxx, xxx)	xx	xxx ± xxx (xxx, xxx)	0.xxxx
Month 8	xx	xxx ± xxx (xxx, xxx)	xx	xxx ± xxx (xxx, xxx)	0.xxxx
Month 9	xx	xxx ± xxx (xxx, xxx)	xx	xxx ± xxx (xxx, xxx)	0.xxxx
Month 10	xx	xxx ± xxx (xxx, xxx)	xx	xxx ± xxx (xxx, xxx)	0.xxxx
Month 11	xx	xxx ± xxx (xxx, xxx)	xx	xxx ± xxx (xxx, xxx)	0.xxxx
Month 12	xx	xxx ± xxx (xxx, xxx)	xx	xxx ± xxx (xxx, xxx)	0.xxxx

Data source: 16.2.9.5 Listing of vital signs

Table 14.3.3.3 LS Means for change in height (cm) from ANCOVA model at Month 12

	Deferiprone	Placebo	Deferiprone Minus Placebo	95% C.I.
N	xx	Xx	xx	
	LS Mean ± SE	LS Mean ± SE	LS Mean ± SE	
Month 12	xxxx ± xxxx	xxxx ± xxxx	xxxx ± xxxx	(xxxx, xxxx)

Data source: 16.2.9.5 Listing of vital signs

Table 14.3.3.4 Trend analysis for height (cm) over time

Rate of change per month	Deferiprone	Placebo	Deferiprone minus Placebo	P-value
Mean ± SE	xxxx ± xxxx	xxxx ± xxxx	xxxx ± xxxx	0.xxxx

Data source: 16.2.9.5 Listing of vital signs

Table 14.3.3.5 Z score analysis for height (cm)

	Deferiprone		Placebo		
	N	Mean ± SD (Min, Max)	N	Mean ± SD (Min, Max)	P-value (t-test)
Baseline	xx	x.x ± x.x (x.x, x.x)	xx	x.x ± x.x (x.x, x.x)	0.xxxx
Month 12	xx	x.x ± x.x (x.x, x.x)	xx	x.x ± x.x (x.x, x.x)	0.xxxx
Change	xx	x.x ± x.x (x.x, x.x)	xx	x.x ± x.x (x.x, x.x)	0.xxxx

Data source: 16.2.9.5 Listing of vital signs

#### 14.3.4      Weight

Table 14.3.4.1 Weight (kg) at each assessment

	Deferiprone		Placebo		P-value (t-test)
	N	Mean ± SD (Min, Max)	N	Mean ± SD (Min, Max)	
Baseline	xx	xxx ± xxx (xxx, xxx)	xx	xxx ± xxx (xxx, xxx)	0xxxx
Month 1	xx	xxx ± xxx (xxx, xxx)	xx	xxx ± xxx (xxx, xxx)	0xxxx
Month 2	xx	xxx ± xxx (xxx, xxx)	xx	xxx ± xxx (xxx, xxx)	0xxxx
Month 3	xx	xxx ± xxx (xxx, xxx)	xx	xxx ± xxx (xxx, xxx)	0xxxx
Month 4	xx	xxx ± xxx (xxx, xxx)	xx	xxx ± xxx (xxx, xxx)	0xxxx
Month 5	xx	xxx ± xxx (xxx, xxx)	xx	xxx ± xxx (xxx, xxx)	0xxxx
Month 6	xx	xxx ± xxx (xxx, xxx)	xx	xxx ± xxx (xxx, xxx)	0xxxx
Month 7	xx	xxx ± xxx (xxx, xxx)	xx	xxx ± xxx (xxx, xxx)	0xxxx
Month 8	xx	xxx ± xxx (xxx, xxx)	xx	xxx ± xxx (xxx, xxx)	0xxxx
Month 9	xx	xxx ± xxx (xxx, xxx)	xx	xxx ± xxx (xxx, xxx)	0xxxx
Month 10	xx	xxx ± xxx (xxx, xxx)	xx	xxx ± xxx (xxx, xxx)	0xxxx
Month 11	xx	xxx ± xxx (xxx, xxx)	xx	xxx ± xxx (xxx, xxx)	0xxxx
Month 12	xx	xxx ± xxx (xxx, xxx)	xx	xxx ± xxx (xxx, xxx)	0xxxx

Data source: 16.2.9.5 Listing of vital signs

Table 14.3.4.2 Change in weight (kg) from baseline to at each follow-up assessment

	Deferiprone		Placebo		
	N	Mean ± SD (Min, Max)	N	Mean ± SD (Min, Max)	P-value (t-test)
Month 1	xx	xxx ± xxx (xxx, xxx)	xx	xxx ± xxx (xxx, xxx)	0.xxxx
Month 2	xx	xxx ± xxx (xxx, xxx)	xx	xxx ± xxx (xxx, xxx)	0.xxxx
Month 3	xx	xxx ± xxx (xxx, xxx)	xx	xxx ± xxx (xxx, xxx)	0.xxxx
Month 4	xx	xxx ± xxx (xxx, xxx)	xx	xxx ± xxx (xxx, xxx)	0.xxxx
Month 5	xx	xxx ± xxx (xxx, xxx)	xx	xxx ± xxx (xxx, xxx)	0.xxxx
Month 6	xx	xxx ± xxx (xxx, xxx)	xx	xxx ± xxx (xxx, xxx)	0.xxxx
Month 7	xx	xxx ± xxx (xxx, xxx)	xx	xxx ± xxx (xxx, xxx)	0.xxxx
Month 8	xx	xxx ± xxx (xxx, xxx)	xx	xxx ± xxx (xxx, xxx)	0.xxxx
Month 9	xx	xxx ± xxx (xxx, xxx)	xx	xxx ± xxx (xxx, xxx)	0.xxxx
Month 10	xx	xxx ± xxx (xxx, xxx)	Xx	xxx ± xxx (xxx, xxx)	0.xxxx
Month 11	xx	xxx ± xxx (xxx, xxx)	Xx	xxx ± xxx (xxx, xxx)	0.xxxx
Month 12	xx	xxx ± xxx (xxx, xxx)	Xx	xxx ± xxx (xxx, xxx)	0.xxxx

Data source: 16.2.9.5 Listing of vital signs

Table 14.3.4.3 LS Means for change in weight (kg) from ANCOVA model at Month 12

	Deferiprone	Placebo	Deferiprone Minus Placebo	95% C.I.
N	xx	xx	xx	
	LS Mean ± SE	LS Mean ± SE	LS Mean ± SE	
Month 12	xxxx ± xxxx	xxxx ± xxxx	xxxx ± xxxx	(xxxx, xxxx)

Data source: 16.2.9.5 Listing of vital signs

Table 14.3.4.4 Trend analysis for weight (kg) over time

Rate of change per month	Deferiprone	Placebo	Deferiprone minus Placebo	P-value
Mean ± SE	xxxx ± xxxx	xxxx ± xxxx	xxxx ± xxxx	0.xxxx

Data source: 16.2.9.5 Listing of vital signs

Table 14.3.4.5 Z score analysis for weight (kg)

	Deferiprone		Placebo		
	N	Mean ± SD (Min, Max)	N	Mean ± SD (Min, Max)	P-value (t-test)
Baseline	xx	x.x ± x.x (x.x, x.x)	Xx	x.x ± x.x (x.x, x.x)	0.xxxx
Month 12	xx	x.x ± x.x (x.x, x.x)	Xx	x.x ± x.x (x.x, x.x)	0.xxxx
Change	xx	x.x ± x.x (x.x, x.x)	Xx	x.x ± x.x (x.x, x.x)	0.xxxx

Data source: 16.2.9.5 Listing of vital signs

### 14.3.5 Concomitant medications

Table 14.3.5.1 Concomitant medications

	Deferiprone (N)	Placebo (N)	Total (N)
Exposure (Patient-years): x.xx		Exposure (Patient- years): x.xx	Exposure (Patient- years): x.xx
Total Patients Reporting: xx		Total Patients Reporting: xx	Total Patients Reporting: xx
Preferred Name	n Patients (%)	n Patients (%)	n Patients (%)
cccccc	x (x.x)	x (x.x)	x (x.x)
cccccc	x (x.x)	x (x.x)	x (x.x)
cccccc	x (x.x)	x (x.x)	x (x.x)
.....	.....	.....	.....

Data source: 16.2.9.9 Listing of concomitant medications

### 14.3.6 Laboratory data

#### 14.3.6.1 Hematology

Table 14.3.6.1.1 Hemoglobin at each assessment

	Deferiprone		Placebo		P-value (t-test)
	N	Mean ± SD (Min, Max)	N	Mean ± SD (Min, Max)	
Baseline	xx	xx.x ± xx.x (xx.x,xx.x)	xx	xx.x ± xx.x (xx.x,xx.x)	0xxxx
Week 1	xx	xx.x ± xx.x (xx.x,xx.x)	xx	xx.x ± xx.x (xx.x,xx.x)	0xxxx
Week 2	xx	xx.x ± xx.x (xx.x,xx.x)	xx	xx.x ± xx.x (xx.x,xx.x)	0xxxx
Week 3	xx	xx.x ± xx.x (xx.x,xx.x)	xx	xx.x ± xx.x (xx.x,xx.x)	0xxxx
Week 4	xx	xx.x ± xx.x (xx.x,xx.x)	xx	xx.x ± xx.x (xx.x,xx.x)	0xxxx
Weekly up to 6 months					
Week 28	xx	xx.x ± xx.x (xx.x,xx.x)	Xx	xx.x ± xx.x (xx.x,xx.x)	0xxxx
Week 30	xx	xx.x ± xx.x (xx.x,xx.x)	Xx	xx.x ± xx.x (xx.x,xx.x)	0xxxx
Week 32	xx	xx.x ± xx.x (xx.x,xx.x)	Xx	xx.x ± xx.x (xx.x,xx.x)	0xxxx
Week 36	xx	xx.x ± xx.x (xx.x,xx.x)	Xx	xx.x ± xx.x (xx.x,xx.x)	0xxxx
Biweekly until termination from the study					

Data source: 16.2.8.1 Listing of hematology

Note: Similar tables will be produced for total WBC count, ANC, MCV, and platelet count.

Table 14.3.6.1.2 Change in hemoglobin from baseline to at each follow-up assessment

		Deferiprone		Placebo		
	N	Mean ± SD (Min, Max)	N	Mean ± SD (Min, Max)	P-value (t-test)	
Week 1	xx	xx.x ± xx.x (xx.x,xx.x)	xx	xx.x ± xx.x (xx.x,xx.x)	0xxxx	
Week 2	xx	xx.x ± xx.x (xx.x,xx.x)	xx	xx.x ± xx.x (xx.x,xx.x)	0xxxx	
Week 3	xx	xx.x ± xx.x (xx.x,xx.x)	xx	xx.x ± xx.x (xx.x,xx.x)	0xxxx	
Week 4	xx	xx.x ± xx.x (xx.x,xx.x)	xx	xx.x ± xx.x (xx.x,xx.x)	0xxxx	
Weekly up to 6 months						
Week 28	xx	xx.x ± xx.x (xx.x,xx.x)	Xx	xx.x ± xx.x (xx.x,xx.x)	0xxxx	
Week 30	xx	xx.x ± xx.x (xx.x,xx.x)	Xx	xx.x ± xx.x (xx.x,xx.x)	0xxxx	
Week 32	xx	xx.x ± xx.x (xx.x,xx.x)	Xx	xx.x ± xx.x (xx.x,xx.x)	0xxxx	
Week 36	xx	xx.x ± xx.x (xx.x,xx.x)	Xx	xx.x ± xx.x (xx.x,xx.x)	0xxxx	
Biweekly until termination from the study						

Data source: 16.2.8.1 Listing of hematology

Note: Similar tables will be produced for total WBC count, ANC, MCV, and platelet count.

Table 14.3.6.1.3 Shift table for hemoglobin at baseline vs last assessment: deferiprone group

		Baseline			P-value (McNemar-Bowker's test)
	N (%)	Low	Normal	High	
Last assessment	Low	xx (xx)	xx (xx)	xx (xx)	0.xxxx
	Normal	xx (xx)	xx (xx)	xx (xx)	
	High	xx (xx)	xx (xx)	xx (xx)	

Data source: 16.2.8.1 Listing of hematology

Note: Similar tables will be produced for total white blood cell (WBC), absolute neutrophil count (ANC), and platelets.

Table 14.3.6.1.4 Shift table for hemoglobin at baseline vs last assessment: placebo group

		Baseline			P-value (McNemar-Bowker's test)
	N (%)	Low	Normal	High	
Last assessment	Low	xx (xx)	xx (xx)	xx (xx)	0.xxxx
	Normal	xx (xx)	xx (xx)	xx (xx)	
	High	xx (xx)	xx (xx)	xx (xx)	

Data source: 16.2.8.1 Listing of hematology

Note: Similar tables will be produced for total white blood cell (WBC), absolute neutrophil count (ANC), and platelets.

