### 1.4 Potential Risks and Benefits

*Risks:* The safety profile of deferiprone in patients with systemic iron overload has been extensively characterized. The most serious adverse event associated with its use is severe neutropenia or agranulocytosis, defined as a confirmed absolute neutrophil count (ANC) less than  $0.5 \times 10^9/L$ . In pooled clinical trials, agranulocytosis has been seen in about 2% of patients. The most common non-serious adverse reactions reported during clinical trials have been nausea, vomiting, abdominal pain, increased alanine aminotransferase, arthralgia, and mild or moderate neutropenia (ANC less than  $1.5 \times 10^9/L$ ).

**Table 1.1** displays the most common adverse drug reactions associated with deferiprone that have been reported in the pooled database of patients with systemic iron overload.

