## 7.2.1.8 Adverse Events of Special Interest

### 7.2.1.8.1 Neutropenia

Individuals taking deferiprone must be monitored for neutropenia, defined as a confirmed absolute neutrophil count (ANC) less than  $1.5 \times 10^9/L$ . Categories of neutropenia are as follows:

Mild neutropenia	A confirmed ANC < $1.5 \times 10^9/L$ but $\geq 1.0 \times 10^9/L$
Moderate neutropenia	A confirmed ANC < $1.0 \times 10^9/L$ but $\geq 0.5 \times 10^9/L$
Severe neutropenia / agranulocytosis	A confirmed ANC < $0.5 \times 10^9/L$

For a case of neutropenia to be confirmed, there must be 2 consecutive counts, a maximum of 3 days apart, that are both less than the specified value. If the 2 counts are not in the same severity category, a third count will be required to determine the severity. If a patient has just a single ANC value less than  $1.5 \times 10^9/L$ , this is to be documented in the CRF as an AE of “decreased ANC”, but is not to be defined as neutropenia. The investigator is to use judgment as to whether the decrease is clinically significant.

In addition to having ANC monitored, participants will be advised to immediately report any symptoms indicative of infection such as fever ( $\geq 38.0^{\circ}C$ ), sore throat, and flu-like symptoms at any time during the study and for one week following the last dose. They will be provided with an emergency services card with contact information, and advised to carry it with them at all times.

Depending on the severity of neutropenia, patients will either remain in or be withdrawn from the study. The management of different severities of neutropenia is described below.

**Mild neutropenia:** A patient who develops mild neutropenia is to interrupt treatment as soon as the neutropenia is confirmed, and ANC is to be monitored every 2 days until resolution.

The patient should re-initiate treatment once the event is resolved, defined as 2 consecutive  $ANC \geq 1.5 \times 10^9/L$ . If ANC is still  $< 1.5 \times 10^9/L$  after 14 days, the investigator is to do the following:

- Withdraw patient from the study and monitor him/her until resolution of the event
- Provide advice regarding protective isolation
- Examine patient the same day (if possible), including drug history and physical examination

- Notify ApoPharma Inc. using the SAE form

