**Moderate neutropenia:** A patient in whom a single ANC measurement  $<1.0 \times 10^9/L$  but  $\geq 0.5 \times 10^9/L$  is detected is to immediately stop treatment, without waiting for confirmation of the count, and a second measurement is to be done within 48 hours. If the second ANC is still  $< 1.0 \times 10^9/L$ , the investigator is to do the following:

- Withdraw patient permanently from the study and monitor ANC daily until resolution
- Provide advice regarding protective isolation
- Examine patient the same day (if possible), including drug history and physical examination
- Notify ApoPharma Inc. using the SAE form

**Severe neutropenia/agranulocytosis:** A patient in whom a single ANC measurement  $< 0.5 \times 10^9/L$  is detected is to immediately stop treatment, without waiting for confirmation of the count, and a second measurement is to be done within 48 hours. If the second ANC is still  $< 0.5 \times 10^9/L$ , the patient is to be permanently withdrawn from the study, and ANC is to be monitored daily until resolution. The following procedures should be done by the investigator or the treating physician, as appropriate:

- Provide protective isolation; if clinically indicated, admit patient to hospital and obtain vital signs every 4 hours
- Examine the patient the same day, if possible, including drug history and physical examination
- With the consent of the parent/guardian (or patient, if applicable), collect a blood sample to attempt to identify genetic or other biomarkers related to agranulocytosis
- Notify ApoPharma Inc. using the SAE form.

The following additional measures describe a suggested medical management and monitoring:

- If possible, consider obtaining bone marrow aspirate for:
  - Histology
  - Progenitor culture
  - Frozen storage (1 mL sample)
- If possible, consider obtaining bone marrow biopsy (minimum length 3 mm)

- Perform septic work-up including chest X-ray, blood, urine, and throat cultures
- Obtain q4h temperatures from patient (monitored by family at home if patient is not in the hospital)
- If warranted, administer granulocyte stimulating factors, such as G-CSF 10 µg/kg, on an in-patient basis if possible, beginning the same day that the ANC is confirmed as  $< 0.5 \times 10^9/L$ ; administer daily until ANC is  $> 1.5 \times 10^9/L$  on 2 consecutive days
- If ANC  $< 0.5 \times 10^9/L$  for 7 days, repeat bone marrow biopsy and aspirate weekly during the period of agranulocytosis, if warranted

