## 5.7 Analysis of Safety

Descriptive statistics (mean, standard deviation, minimum, and maximum) will be produced for continuous variables, and frequency tables will be produced for discrete variables by treatment group. Summaries of adverse events and serious adverse events will be produced by treatment group. Shift tables will be generated for comparing the screening/baseline values and end of study values of the relevant measures.

The following safety data will be summarized by treatment group:

- Adverse events (AEs), adverse drug reactions (ADRs), serious adverse events (SAEs), and serious adverse drug reactions (SADRs)
- Number of discontinuations due to AEs
- Hematology assessments
- Biochemistry assessments
- Urinalysis
- Vital signs
- Prior and concomitant medications

Prolactin is measured at baseline and Month 12. The change in prolactin level from baseline to Month 12 will be compared between the two treatment groups using an ANCOVA model with baseline value as a covariate and treatment as the main factor.

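### The ANC shift tables compare baseline with an undefined last count, one arm at a time, so a resolved mild neutropenia almost never shows, and no table gives each child's worst ANC by arm

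*SAP*

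**What the plan says.** SAP section 5.7 sets the general rule: "Shift tables will be generated for comparing the screening/baseline values and end of study values of the relevant measures". The shells in SAP 14.3.6.1 apply it as "Table 14.3.6.1.3 Shift table for hemoglobin at baseline vs last assessment: deferiprone group", followed by Table 14.3.6.1.4 for placebo. The rows and columns are Low, Normal and High, and each table has one P value, from McNemar-Bowker's test. The note beneath reads "Similar tables will be produced for total white blood cell (WBC), absolute neutrophil count (ANC), and platelets". The biochemistry shells in 14.3.6.2 have the same form. The SAP defines neither the last assessment nor the limits for Low and High.

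Protocol 1.4 says of deferiprone: "The most serious adverse event associated with its use is severe neutropenia or agranulocytosis". Protocol 7.2.1.8.1 then treats the grades differently:

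- Mild: treatment is interrupted and "ANC is to be monitored every 2 days until resolution". On restarting: "The patient should re-initiate treatment once the event is resolved, defined as 2 consecutive" counts of at least 1.5 x 10^9/L. A child still below 1.5 after 14 days is withdrawn and followed until the event resolves.
- Moderate, once confirmed: "Withdraw patient permanently from the study and monitor ANC daily until resolution".
- Severe, once confirmed: also permanent withdrawal with daily counts until resolution.

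For ALT and AST, SAP Tables 14.3.6.2.5 and 14.3.6.2.6 count children who exceeded 2, 3 or 5 times the upper limit at any time on study, with Fisher's test between arms. ANC has no such table.

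**The concern.** Safety is the secondary objective, and neutropenia is the hazard that drives the weekly and fortnightly blood counts. A shift table that keeps one post-baseline count per child discards what those counts were taken to find. ANC falls, treatment stops and ANC recovers, so the final count is the least likely to be informative.

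For a withdrawn child the entry depends on an undefined term. The candidates are the count that led to withdrawal, the count at the early termination visit, and the counts taken afterwards until recovery. The same agranulocytosis could be filed as Low under one choice and Normal under another. Even when it shows as Low, the grade can be lost: counts of 1.4 and 0.3 can share a cell.

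The P value in these tables asks whether shifts within one arm are symmetric. It does not compare deferiprone with placebo.

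**Working it through.** **Inputs.**
- 32 children per arm (Protocol 4.1).
- Pooled rates in Protocol Table 1.1: neutropenia 54 of 860, agranulocytosis 18 of 860. These reproduce: 54/860 = 6.3% and 18/860 = 2.1%.
- Counts weekly to Month 6, then every two weeks (SAP 4.2.2).
- The 14-day limit for unresolved mild neutropenia (Protocol 7.2.1.8.1).

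The documents attach no figure to the shift table itself, so there is nothing further to reproduce.

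**1. Counts used.** About 26 weekly plus 13 fortnightly counts make 39 scheduled post-baseline counts for a child who completes. The shift table uses one.

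**2. Chance that a resolved mild episode shows.** Assume one episode of d days at a random time in 360 days, visible only if it covers the last count. The chance is d/360.
- d = 4: 4/360 = 1.1%
- d = 14: 14/360 = 3.9%

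The 14-day case reflects the protocol limit. The 4-day case and the random timing are assumptions.

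**3. Expected cases on deferiprone.** Assume the pooled rates carry over to these children and 12 months, which the documents do not say.
- Neutropenia: 32 x 54/860 = 2.0; chance of at least one = 1 - (1 - 54/860)^32 = 87%.
- Agranulocytosis: 32 x 18/860 = 0.7; chance of at least one = 49%.

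**4. How many of 2 neutropenia cases the planned table would show.** With d = 14:
- Both mild and resolved: 2 x 14/360 = 0.08 children.
- One resolved, one withdrawn, follow-up to recovery included: 1 x 14/360 + 0 = 0.04.
- One resolved, one withdrawn, the low exit count taken as last: 1 x 14/360 + 1 = 1.04.

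The last two lines differ only in the meaning given to the last assessment.

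**5. The within-arm test.** If m children shift from Normal to Low and none the other way, the Bowker statistic is m.
- 1 degree of freedom: m = 2 gives p = 0.16; m = 4 is needed (p = 0.046).
- 3 degrees of freedom: m = 2 gives p = 0.57; m = 8 is needed (p = 0.046).

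Even if every case expected at 6.3% were low at the last count, the chance of 4 or more among 32 is about 14%.

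**6. Number of within-arm P values.** Hematology has 4 parameters (hemoglobin, WBC, ANC, platelets). Biochemistry has 15 (albumin plus 14 in the note, counting three bilirubins). So (4 + 15) x 2 arms = 38.

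**7. What a between-arm table could test.** Fisher's exact test, two-sided, 32 per arm: 2 against 0 gives p = 0.49; 5 against 0 gives p = 0.053; 6 against 0 gives p = 0.024.

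**The case against.** The strongest reply is that neutropenia is reported elsewhere. Protocol 7.2.1.8.1 requires even a single ANC below 1.5 to be recorded as an adverse event, so every detected low count should reach the adverse event tables. SAP 5.7.1 compares each term between arms by Fisher's test, and tables by maximum severity and rates per 100 patient-years are planned. Tables 14.3.6.1.1 and 14.3.6.1.2 give ANC at each assessment with minimum and maximum per arm. Figure 14.3.1.2 shows the proportion abnormal, Figures 14.3.1.3 and 14.3.1.4 plot individual cases, and Listings 16.2.8.1a and 16.2.8.1b cover abnormal and clinically significant values. The shells are also indicative, and tables may be added.

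This stands, and it limits the point to the laboratory summary. It does not fill the gap. Adverse event terms split low counts: a single value is recorded as decreased ANC and a confirmed one as neutropenia, and Table 1.1 shows such terms in different organ classes. No planned row brings them together or grades them by measured ANC. By-visit displays spread brief episodes over many time points.

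The objection is also right about a simple table of lowest counts. The protocol does not let a single low value be called neutropenia. Children leave once ferritin is at least 1000 µg/L at two consecutive visits, and the design expects 70% on deferiprone and 20% on placebo to be below that level at Month 12. Placebo children would therefore tend to leave earlier and have fewer counts, which by itself makes the worst value look worse on deferiprone.

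**Conclusion.** The point holds as a weakness of one set of laboratory tables, of minor to moderate weight. A resolved mild episode is almost always invisible in the planned ANC shift table (about 1% to 4% visible under the stated assumption). A child withdrawn for neutropenia is classified by an undefined rule. No planned table gives the worst ANC per child by arm, although ALT and AST have an equivalent.

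A reader might infer more, and the documents do not support it:

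- That the drug's main risk disappears from the safety report. It does not; the adverse event tables, figures and listings carry it.
- That the restart rule hides agranulocytosis. Restart after recovery applies to mild neutropenia only. Confirmed moderate and severe cases are withdrawn, and whether they show depends on the undefined last assessment.
- That every child who restarts ends with a normal count. A relapse can cover the last count, and the shell's Normal is not stated to mean 1.5 or above.
- That the within-arm tests give up to a 25% risk of a false contrast for ANC. With the same true shift in both arms, the chance that only deferiprone is significant is p(1 - p), which reaches 0.25 only at 50% power per arm. An ANC table that is nearly empty is far from that.

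The case counts rest on the pooled rates applying here. They show scale and are not a forecast.

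**What to change.** 1. Define the last assessment in the SAP as either the last on-treatment count or the last available count.
2. Keep the end-of-study shift and add a table from baseline to worst post-baseline ANC, including unscheduled and follow-up counts. Use the protocol's cut-offs: at least 1.5, 1.0 to below 1.5, 0.5 to below 1.0, and below 0.5 x 10^9/L. Report any single low count separately from neutropenia confirmed under Protocol 7.2.1.8.1.
3. Show both arms side by side with n (%), the difference and an exact 95% confidence interval. Give patient-years or the number of counts per arm beside it, because of the earlier exit expected on placebo. Patient-years is the cleaner choice, since a low count itself triggers extra counts.
4. Remove the 38 McNemar-Bowker P values from the hematology and biochemistry shift tables.

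The cost is a sentence of definition, one derived variable and one table, on counts already collected. The new table is descriptive, is not powered to test a difference, and should be labelled so.
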